10.2.2 Adverse Event Overview

An overview of AEs will be presented by treatment period consisting of the number and percentage of subjects experiencing at least one event for each of the following AE categories:

- Any treatment-emergent AE
- Any treatment-emergent AE related to study treatment according to the investigator
- Any severe treatment-emergent AE
- Any serious treatment-emergent AE
- Any treatment-emergent AE leading to discontinuation of study treatment
- Any treatment-emergent AE leading to death
- All deaths

10.2.3 Treatment-Emergent Adverse Events by SOC and/or PT

Treatment-emergent adverse events will be summarized by treatment group, for each treatment period and overall, by SOC and PT; by maximum relationship to study treatment as assessed by the investigator (e.g., reasonable possibility or no reasonable possibility) and SOC and PT; by maximum severity and SOC and PT; and by subject number and SOC and PT. Specific adverse events will be counted once for each subject for calculating percentages, unless stated otherwise. In addition, if the same adverse event occurs multiple times within a subject, the highest severity and level of relationship to investigational product will be reported.

The incidence of common ($\geq 2\%$ of subjects in any treatment group) TEAEs will be summarized by preferred term, and treatment group. A similar 5% table will be provided as well.

10.2.4 Deaths, Serious Adverse Events, and Adverse Events Leading to Study Treatment Discontinuation

Treatment-emergent serious adverse events (TESAEs) and TEAEs leading to premature discontinuation of study treatment will be summarized by SOC and PT for each treatment period. TESAEs will also be summarized by SOC and PT overall.

For TEAEs leading to premature discontinuation of study treatment, summaries by SOC and PT will be provided as follows:

- TEAEs with start date and treatment discontinuation date in the double-blind period
- TEAEs with start date and treatment discontinuation date in the extension period
- TEAEs leading to treatment discontinuation during the extension period, i.e., the treatment discontinuation date occurred in the extension period regardless of whether the TEAE started in the double-blind period or the extension period.

Tabular listings will be provided for all deaths, all SAEs and TEAEs leading to premature discontinuation of study treatment.

10.2.5 Adverse Events of Special Interest

Adverse events of special interest are categorized as follows:

- Treatment-emergent suicidal ideations with intent, with or without a plan, (ie, Type 4 or 5 on the C-SSRS) or any suicidal behaviors.
- Treatment-emergent elevated ALT or AST lab value $\geq 3 \times \text{ULN}$.
- Potential Hy's law cases: elevated ALT or AST lab value that is $\geq 3 \times \text{ULN}$ and an elevated total bilirubin lab value that is $\geq 2 \times \text{ULN}$ and, at the same time, an alkaline phosphatase lab value that is $< 2 \times \text{ULN}$.
- Related summaries can be found in C-SSRS summary tables and lab section.

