5.6 Follow-Up After Subject Discontinuation of Study Drug or from Study

Subjects will be followed for 30 days following discontinuation of the study drug. The 30-day follow-up visit should not take place sooner than 30 days after the last dose of the study drug. The allowable visit window is +3 days (30 to 33 days after the last study drug date).

Notification of early subject discontinuation from the study/study drug and the reason for discontinuation should be made to the sponsor and should be documented on the appropriate case report form. All randomized subjects who prematurely discontinue from the study/study drug, regardless of cause, should be seen for final study assessments. The final assessments should be defined as completion of the evaluations scheduled for the ET and the Follow-up visits.

In the event a subject withdraws consent from the clinical study, biomarker research will continue unless the subject explicitly requests analysis to be stopped. When AbbVie is informed the subject has withdrawn and no longer wishes biomarker research to continue, samples will not be analyzed, no new biomarker analysis data will be collected for the withdrawn subject or added to the existing data or database(s), and the samples should be destroyed. A subject may withdraw consent for optional biomarker research at any time and remain in the clinical study. Data generated from clinical study and/or optional biomarker research, before subject withdrawal of consent, will remain part of the study results.

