SUSAR	Refers to individual SAE case reports from clinical trials where a causal relationship between the SAE and the IMP was suspected by either the sponsor or the investigator, is unexpected (not listed in the applicable RSI), and meets one of the above serious criteria.

AbbVie will be responsible for SUSAR reporting for the IMP in accordance with global and local requirements, including reporting to Eudravigilance database in accordance with EU Clinical Trial Regulation.

AEs will be monitored throughout the study to identify any of special interest that may indicate a trend or risk to subjects.

Adverse Events of Special Interest

The following AEs of special interest will be monitored during the study:

- Treatment-emergent suicidal ideations with intent, with or without a plan, (i.e., Type 4 or 5 on the C-SSRS) or any suicidal behaviors.
- Treatment-emergent elevated ALT or AST laboratory value $\geq 3 \times \text{ULN}$.
- Potential Hy's Law cases: elevated ALT or AST laboratory value $\geq 3 \times \text{ULN}$ and an elevated total bilirubin laboratory value $\geq 2 \times \text{ULN}$ and, at the same time, an alkaline phosphatase laboratory value $< 2 \times \text{ULN}$.

Adverse Event Severity and Relationship to Study Drug

The investigators will rate the severity of each AE as mild, moderate, or severe. The investigator will use the following definitions to rate the severity of each AE:

Mild	The AE is transient and easily tolerated by the subject.
Moderate	The AE causes the subject discomfort and interrupts the subject's usual activities.
Severe	The AE causes considerable interference with the subject's usual activities and may be incapacitating or life threatening.

The investigator will use the following definitions to assess the relationship of the AE to the use of study drug:

Reasonable Possibility	After consideration of factors including timing of the event, biologic plausibility, clinical judgment, and potential alternative causes, there is sufficient evidence (information) to suggest a causal relationship.
No Reasonable Possibility	After consideration of factors including timing of the event, biologic plausibility, clinical judgment, and potential alternative causes, there is insufficient evidence (information) to suggest a causal relationship.

Pregnancy

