APPENDIX H. ACTIVITY SCHEDULE

The following tables show the required activities. The individual activities are described in detail in the **Operations Manual** ([Appendix J](#)).

Table 3. Schedule of Activities

Activity	Screening period (4 weeks)	Double Blind Treatment Period (12 weeks)				Active Treatment Extension Period (dose blinded, 12 weeks)			Follow up Period (30 days)
	Visit 1/ Screening/ Baseline	Visit 2	Visit 3	Visit 4	Visit 5/ ET DB	Visit 6	Visit 7	Visit 8/ ET EX	Visit 9/EOS
	Week 4 (Day 35 to Day 28)	Day 1	Week 4 (Day 28) ± 3 days	Week 8 (Day 56) ± 3 days	Week 12 (Day 84) + 3 days	Week 16 (Day 112) ± 3 days	Week 20 (Day 140) ± 3 days	Week 24 (Day 168) + 3 days	Week 28 (Day 198/ 30 days after the last dose of study drug) + 3 days
INTERVIEWS & QUESTIONNAIRES									
Informed consent	✓								
Informed consent for biomarker research (optional)	✓								
Eligibility criteria	✓	✓							
Demographics	✓								
Medical history	✓								
Migraine headache history	✓								
Review prior medications including all migraine prophylactic medication use	✓								
Menstrual cycle assessment	✓	✓	✓	✓	✓	✓	✓	✓	✓
Adverse events	✓	✓	✓	✓	✓	✓	✓	✓	✓
Concomitant medications/concurrent procedures	✓	✓	✓	✓	✓	✓	✓	✓	✓
Provide eDiary, instructions and training	✓								
eDiary data collection	✓	✓	✓	✓	✓				
Collect eDiary device		✓			✓				
Review of eDiary data and compliance		✓	✓	✓	✓				

Activity	Screening period (4 weeks)	Double Blind Treatment Period (12 weeks)				Active Treatment Extension Period (dose blinded, 12 weeks)			Follow up Period (30 days)
	Visit 1/ Screening/ Baseline	Visit 2	Visit 3	Visit 4	Visit 5/ ET DB	Visit 6	Visit 7	Visit 8/ ET EX	Visit 9/EOS
	Week 4 (Day 35 to Day 28)	Day 1	Week 4 (Day 28) ± 3 days	Week 8 (Day 56) ± 3 days	Week 12 (Day 84) + 3 days	Week 16 (Day 112) ± 3 days	Week 20 (Day 140) ± 3 days	Week 24 (Day 168) + 3 days	Week 28 (Day 198/ 30 days after the last dose of study drug) + 3 days
C SSRS (eTablet)	✓	✓	✓	✓	✓	✓	✓	✓	✓
ASC 12 (eTablet)	✓								
HIT 6 (eTablet)		✓	✓	✓	✓				
PGIC (eTablet)					✓				
PGI S (eTablet)		✓	✓	✓	✓				
WPAI:MIGRAINE (eTablet)		✓	✓	✓	✓				
PSSM (eTablet)			✓	✓	✓				
EQ 5D 5L (eDiary)	✓	✓	✓	✓	✓				
MIDAS (eTablet)		✓			✓				
MSQ v2.1 (eTablet)		✓	✓	✓	✓				
PROMIS PI (eTablet)		✓	✓	✓	✓				
PHQ 9 (eTablet)		✓			✓				
 LOCAL LABS & EXAMS									
Physical examination	✓				✓			✓	✓
Height (Visit 1 only) and weight	✓	✓	✓	✓	✓	✓	✓	✓	✓
Vital sign measurements	✓	✓	✓	✓	✓	✓	✓	✓	✓
12 lead ECG	✓				✓			✓	

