10.5.2 Columbia-Suicide Severity Rating Scale

For C-SSRS, the number and percentage of subjects with suicidal ideation or suicidal behavior as recorded on the C-SSRS will be summarized by treatment group for the Safety Populations 1 and 2. The distribution of responses for most severe suicidal ideation and most severe suicidal behavior in the subject's lifetime history, in the past 6 months, in the double-blind treatment period, active treatment extension period, and in the follow up period will also be presented by treatment group. Supportive listings will be provided and

will include the PID number, study center number, treatment group, lifetime history, and postbaseline values. Intensity of suicidal ideation and suicidal behavior type will also be included in these listings.

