13.0 Version History

Table 4. SAP Version History Summary

Version	Date	Summary
1.0	18 March 2020	Initial version
2.0	25 September 2023	This version of the SAP was completely re-written based on Protocol Amendment 5.
3.0	22 October 2024	
Corrected typos and inconsistencies throughout the document.
 
Removed the listing for positive urine pregnancy test per AbbVie CSR simplification standard.
 
For Japan submission purpose
 
 Section 3.3 added endpoints CFS in monthly headache days with nausea and/or vomiting symptom, photophobia and phonophobia Section 9.6 added efficacy subgroup analyses: number of migraine prevention medication failures with proven efficacy (category details below), migraine with or without aura diagnosis (migraine with aura, migraine without aura, and migraine both with and without aura), and prior exposure to calcitonin gene-related peptide (CGRP) antagonists (yes/no) 
Removed AESI summary by SOC and PT as data is not collected in the AE eCRF. Updated the text to refer to C-SSRS and lab section for summary.
 
Removed temperature from vital sign summary.
 
Updated SI unit and PCS low for estimated glomerular filtration rate in Table C-1 per standard lab transfer unit.
 
Added more details in estimand description and handling of the intercurrent events in Section 2.1, Section 9.3.2, and Section 9.4.2.

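### The suicidality AESI covers any suicidal behaviour but is summarised only from C-SSRS records, so a suicide, or a known attempt with no later C-SSRS, is not counted in that summary

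*SAP*

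**What the plan says.** Protocol 6.1 lists as an AESI: "Treatment-emergent suicidal ideations with intent, with or without a plan, (i.e., Type 4 or 5 on the C-SSRS) or any suicidal behaviors". SAP 10.2.5 repeats the definition. It specifies no AESI table of its own and refers the reader elsewhere: "Related summaries can be found in C-SSRS summary tables and lab section".

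For suicidality, that leads to SAP 10.5.2, where "the number and percentage of subjects with suicidal ideation or suicidal behavior as recorded on the C-SSRS will be summarized by treatment group", for Safety Populations 1 and 2. The same section presents the most severe ideation and the most severe behaviour for lifetime history, the past 6 months, and then "in the double-blind treatment period, active treatment extension period, and in the follow up period".

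SAP 13.0 gives a reason for having no AESI table by SOC and PT: "Removed AESI summary by SOC and PT as data is not collected in the AE eCRF".

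**The concern.** The definition and the data source have different scope. The behaviour half of the definition does not require that the behaviour was entered on a C-SSRS form. The summary does require it.

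The same routing works for the other two AESIs. Both are defined by laboratory values, so the laboratory section holds every qualifying case. Suicidal behaviour is a clinical event that can reach the site as an adverse event or a death, with no questionnaire completed afterwards.

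Any such loss is informative. The most severe outcome in the category, death, is the one least likely to be followed by a form, while the subject's earlier negative forms stay in the table. The suicidality display could then show no case in an arm whose death or SAE listing contains one. With events this rare, a single case may be the whole result.

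**Working it through.** The plan states no figure on this point, so the check traces each type of case through the planned outputs.

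**1. Is there a second source?** SAP 10.2.5 points to the C-SSRS tables, and 10.5.2 limits them to C-SSRS records. SAP 10.2.1 to 10.2.4 summarise adverse events by SOC and PT, but nothing there feeds back into the suicidality AESI. Nor does 10.5.2 specify one by-arm count of Type 4/5 ideation or any behaviour. It gives any ideation or behaviour, plus the two severity distributions.

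**2. When is a C-SSRS due?** Protocol Appendix H, Table 3, schedules it at all nine visits, including Visit 5/ET DB, Visit 8/ET EX and Visit 9. Table 4 keeps it for remote visits. For early leavers, Protocol 5.6 says: "All randomized subjects who prematurely discontinue from the study/study drug, regardless of cause, should be seen for final study assessments". It adds: "The final assessments should be defined as completion of the evaluations scheduled for the ET and the Follow-up visits". An attempt that leads to withdrawal is therefore normally followed by two more forms.

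**3. How long are the scheduled gaps?** Longest gap = (later visit day + its upper window) − (earlier visit day − its lower window).

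| Visits | Nominal (days) | Longest (days) |
|---|---|---|
| 2 to 3 | 28 − 1 = 27 | (28 + 3) − 1 = 30 |
| 3 to 4 | 56 − 28 = 28 | (56 + 3) − (28 − 3) = 34 |
| 4 to 5 | 84 − 56 = 28 | (84 + 3) − (56 − 3) = 34 |
| 5 to 6 | 112 − 84 = 28 | (112 + 3) − 84 = 31 |
| 6 to 7 | 140 − 112 = 28 | (140 + 3) − (112 − 3) = 34 |
| 7 to 8 | 168 − 140 = 28 | (168 + 3) − (140 − 3) = 34 |
| 8 to 9 | 198 − 168 = 30 | (198 + 3) − 168 = 33 |

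These are intervals between forms, not periods in which an act goes unrecorded. Assuming that each post-dose form asks about the time since the last one, an act is missed only if no later form is completed.

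**4. Which cases are left?** Two kinds: a death with no form completed afterwards, and an attempt known to the site in a subject who attends neither the early termination nor the follow-up visit.

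**5. Where else would they appear?** SAP 10.2.2 tabulates serious events, events leading to death and all deaths. SAP 10.2.3 gives the full SOC/PT tables, and 10.2.4 gives the serious-event and discontinuation tables with listings. The common-event tables in 10.2.3 would not show a single case: 2% of 130 is 2.6, so at least 3 subjects with the same preferred term are needed.

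**6. What is the size of one missed case?** Inputs: 130 per arm (SAP 2.3) and exact two-sided 95% Clopper-Pearson limits.
- Counted: 1/130 = 0.77%, upper limit 4.2%.
- Missed: 0/130 = 0%, upper limit 1 − 0.025^(1/130) = 2.8%.

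**7. How many subjects could lack a later form?** The planned double-blind dropout is 5.4% (SAP 2.4): 0.054 × 130 = 7.0 per arm, or 0.054 × 520 = 28.1 overall. The share of them without an early termination C-SSRS is not given, nor is any suicidality rate. The expected number of missed cases cannot be computed.

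**The case against.** The strongest reply is that nothing is lost. A suicide or serious attempt is an SAE, appears in several planned tables and listings, and is seen by a DSMB that reviews unblinded safety data. At such low counts each case would be examined individually. This stands, and it limits the point to the AESI display.

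A second reply is that a C-SSRS-based summary is a fair reading. The AESI sentence names the scale, and the withdrawal rule in Protocol 5.5 ties behaviour to the scale's behaviour section. SAP 10.2.5 also only cross-refers, without saying that the adverse event outputs are to be ignored. This has some force. But the definition's behaviour limb is open-ended, and the reader is given no other place to find the AESI result.

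Several stronger readings are tempting but not supported:
- **Any attempt that ends participation goes uncounted because forms are completed only every 4 weeks.** Early termination and follow-up forms are scheduled, and early leavers are to be called back for both.
- **Hospitalisation removes the subject.** No section says that it ends participation or cancels later forms.
- **The SAP used to combine C-SSRS and adverse event data.** The version history says only that a SOC/PT summary was removed.

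**Conclusion.** The point holds in a narrow form. As written, the SAP would leave a completed suicide, or a known attempt with no later C-SSRS, out of the suicidality AESI summary. Overall safety reporting would still contain it.

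The likely number of such cases is small. Protocol 5.1 excludes subjects with Type 4/5 ideation or suicidal behaviour in the past 6 months, and 0 to 1 event per arm is a reasonable assumption, though the documents give no rate. One missed case would move an arm from 0.8% to 0%, and the exact upper limit from 4.2% to 2.8%.

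The conclusion assumes that no form is completed on a subject's behalf after a death. The Operations Manual, which may cover this, is not among the documents. If it requires such a form, the gap shrinks to subjects who attend neither visit. This is a worthwhile low-cost improvement; it does not threaten the trial's conclusions.

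**What to change.** In SAP 10.2.5 and 10.5.2, define the reported suicidality AESI, by arm and period, as a subject with either:
- Type 4/5 ideation or any suicidal behaviour on any post-dose C-SSRS, including the early termination and follow-up forms; or
- a TEAE, SAE or death coded to a pre-listed set of MedDRA terms for suicidal behaviour or suicidal ideation with intent.

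Count each subject once, and show in the listing which source or sources identified the case. Assign adverse events to periods by the existing rules in SAP 10.2.1. Fix the term list before unblinding. Leave the C-SSRS tables unchanged.

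The cost is SAP wording, a term list, one extra table and medical review of borderline terms. Adverse events are already collected and coded in MedDRA, so no new data are needed.

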10.3 Analysis of Laboratory Data

The clinical laboratory tests defined in the protocol operations manual (e.g., hematology, clinical chemistry, and urinalysis) will be summarized.

Each laboratory variable will be summarized by treatment group for all time points (starting with Baseline) with the number of non-missing observations, mean and standard deviation, median, Q1, Q3, minimum and maximum. Mean change from baseline to each applicable post-baseline visit will be summarized for selected laboratory variables, with the number of observations, baseline mean, and visit mean. In addition, descriptive statistics for values and changes from the baseline values in conventional units at each assessment time point will be presented for selected clinical laboratory parameters listed in [Appendix D](#). A description of reporting the lab values in conventional units in patient narratives (along with the standard reporting in SI units) is presented at the end of [Appendix D](#).

Laboratory abnormalities will be evaluated based on Potentially Clinically Significant (PCS) criteria ([Appendix C](#), Table C-1). For each laboratory PCS criterion, the number

and percentage of subjects who have a laboratory value meeting the criteria will be summarized by treatment group. Listings will be provided to summarize subject-level laboratory data for subjects meeting PCS criteria.

The number and percentage of subjects meeting each of the criteria for postbaseline hepatic laboratory abnormalities listed in [Appendix C](#), Table C-2 will be summarized. The percentages will be calculated relative to the number of subjects with at least 1 available postbaseline assessment. The numerator will be the total number of subjects having at least 1 postbaseline value that meets the specific category during the study. A supportive listing will also be provided.

The number and percentage of subjects with an adjudicated case (i.e., $ALT \geq 3 \times ULN$ and/or $AST \geq 3 \times ULN$) will be summarized by treatment group and by relationship of ALT or AST elevation to study medication. The percentages will be calculated relative to the number of subjects with at least 1 adjudicated case. The numerator will be the number of subjects with at least 1 adjudicated case in the specific category of relationship. If a subject has more than 1 adjudicated case, he or she will be counted in the most relevant category of relationship.

Subjects with an adjudicated case (i.e., $ALT \geq 3 \times ULN$ or $AST \geq 3 \times ULN$) will be listed with their ALT and AST assessments, adjudication dates, relationship of ALT or AST elevation to study medication, and confounding factor(s). Additional listings will be provided for subjects who meet $ALT \geq 3 \times ULN$ or $AST \geq 3 \times ULN$ and/or potential Hy's law and have one of the following categories: at least 1 abnormal liver biochemistry risk factor, at least 1 liver disease sign and symptom, at least 1 liver diagnostic test performed, consultation with a specialist for liver evaluation, liver lab tests performed, and drug screen performed, respectively.

Potential Hy's Law criteria within a 24-hour window is defined by a postbaseline evaluation of alanine aminotransferase (ALT) or aspartate aminotransferase (AST) $\geq 3 \times ULN$, along with total bilirubin (TBL) $\geq 2 \times ULN$ and a non-elevated alkaline phosphatase (ALP) $< 2 \times ULN$, all based on blood draws collected within a

24-hour period. Patients who meet the potential Hy's Law criteria from the first dose of study drug to the end of study will be summarized. Supportive tabular displays will also be provided.

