5.10 External Committees

Data Safety Monitoring Board (DSMB)

An external DSMB composed of clinicians and statisticians independent of AbbVie and with relevant expertise in their field will review unblinded data from the ongoing study. The DSMB is responsible for safeguarding the interests of trial subjects, assessing the safety of the interventions during the trial, as well as for monitoring the integrity and interpretability of the trial. The DSMB will provide recommendations to the sponsor, including modification or ET of the study, if emerging data show unexpected and clinically significant AEs of treatment.

In order to maintain sponsor blinding, an external statistical data analysis center is responsible for performing the analyses described in the DSMB charter as well as additional analyses requested by the DSMB and facilitating interpretation and answering questions that arise before, during or after DSMB review.

The DSMB will regularly review unblinded safety data from the ongoing study according to the schedule provided in the DSMB charter, including as appropriate, AEs, laboratory values, vital sign, values, and ECG results.

A separate DSMB charter will be prepared outside of the protocol and will further describe the roles and responsibilities of the DSMB members, frequency and scope of the data reviews, and expectations for blinded communications.

Hepatic Events Adjudication Committee

A Hepatic Events Adjudication Committee Charter should be established and should describe the process for the blinded surveillance, monitoring, and adjudication by the Hepatic Events Adjudication Committee of events of post-treatment elevations of ALT and/or AST $\geq 3 \times$ ULN in the atogepant program. The purpose of this committee charter should be to provide a standardized process for the adjudication of data associated with these events in order to determine whether the elevation was related to atogepant.

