2.3 Treatment Assignment and Blinding

On Study Day 1 of the Double-Blind Treatment Period, approximately 520 subjects will be randomized to one of the following 4 arms in a 1:1:1:1 ratio:

- Placebo (n = 130)
- Atogepant 10 mg (n = 130)
- Atogepant 30 mg (n = 130)
- Atogepant 60 mg (n = 130)

The study will be enrolled so that approximately 70% of randomized subjects will have taken at least 1 prior migraine prevention medication with proven efficacy.

Randomization will be stratified by site and by prior exposure (yes/no) to a migraine prevention medication with proven efficacy.

After finishing the double-blind treatment period, completers in the placebo arm will be re-randomized to atogepant 10 mg, atogepant 30 mg, or atogepant 60 mg arm (dose blinded) in a 1:1:1 ratio in the active treatment extension period.

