4.0 Analysis Populations

The following population sets will be used for the analyses.

The Screened Population consists of all subjects who signed informed consent.

The Intent-to-Treat (ITT) population includes all randomized subjects.

All efficacy analyses will be performed using the modified Intent-to-Treat (mITT) population, consisting of all randomized subjects who received at least 1 dose of study drug, had an evaluable baseline period of eDiary data and had at least 1 evaluable post-baseline 4-week period (Weeks 1 to 4, 5 to 8, and 9 to 12) of eDiary data. Refer to SAP [Appendix B](#) for the definition of evaluable baseline and post-baseline period. For efficacy analyses, subjects will be included in the analysis according to the treatment group to which they were randomized (as randomized).

All safety analyses will be performed using the Safety Populations: Safety population 1 and Safety population 2. Safety Population 1 consists of all subjects who received at least 1 dose of study drug during the double-blind treatment period. Safety Population 2 consists of all subjects who received at least 1 dose of study drug during the active treatment extension period. For safety data analyses, the subjects will be analyzed according to actual treatment received (rather than as randomized). A subject's actual treatment will be determined by the first dose of study treatment.

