	Red blood cell count	$10^{12}/L$	$< 0.9 \times LLN$	$> 1.1 \times ULN$
	White blood cell count	$10^9/L$	$< 0.9 \times LLN$	$> 1.5 \times ULN$
Urinalysis	pH	pH	$< 0.9 \times LLN$	$> 1.1 \times ULN$
	Glucose	mmol/L	—	Positive ¹
	Protein	g/L	—	Positive ²
	Specific gravity	—	—	$> 1.1 \times ULN$

LLN = lower limit of normal value; ULN = upper limit of normal value; normal value provided by laboratory.

SI = Le Système International d'Unités (International System of Units).

- Any results other than negative will be considered as positive.
- Any results other than trace or negative will be considered as positive.

Table C-2. Criteria for Hepatic Laboratory Abnormalities

Laboratory Parameter	Categories
ALT	$\geq 1 \times ULN$
	$\geq 1.5 \times ULN$
	$\geq 2 \times ULN$
	$\geq 3 \times ULN$
	$\geq 5 \times ULN$
	$\geq 10 \times ULN$
	$\geq 20 \times ULN$

Laboratory Parameter	Categories
AST	$\geq 1 \times \text{ULN}$ $\geq 1.5 \times \text{ULN}$ $\geq 2 \times \text{ULN}$ $\geq 3 \times \text{ULN}$ $\geq 5 \times \text{ULN}$ $\geq 10 \times \text{ULN}$ $\geq 20 \times \text{ULN}$
ALT or AST	$\geq 1 \times \text{ULN}$ $\geq 1.5 \times \text{ULN}$ $\geq 2 \times \text{ULN}$ $\geq 3 \times \text{ULN}$ $\geq 5 \times \text{ULN}$ $\geq 10 \times \text{ULN}$ $\geq 20 \times \text{ULN}$
Bilirubin Total	$\geq 1 \times \text{ULN}$ $\geq 1.5 \times \text{ULN}$ $\geq 2 \times \text{ULN}$ $\geq 3 \times \text{ULN}$ $\geq 5 \times \text{ULN}$ $\geq 10 \times \text{ULN}$ $\geq 20 \times \text{ULN}$
Alkaline Phosphatase	$\geq 1 \times \text{ULN}$ $\geq 1.5 \times \text{ULN}$ $\geq 2 \times \text{ULN}$ $\geq 3 \times \text{ULN}$ $\geq 5 \times \text{ULN}$ $\geq 10 \times \text{ULN}$ $\geq 20 \times \text{ULN}$
Concurrent Elevations ¹	ALT or AST $\geq 3 \times \text{ULN}$ and Bilirubin Total $\geq 1.5 \times \text{ULN}$ ALT or AST $\geq 3 \times \text{ULN}$ and Bilirubin Total $\geq 2 \times \text{ULN}$

Laboratory Parameter	Categories
Potential Hy's Law ¹	ALT or AST $\geq 3 \times$ ULN and Bilirubin Total $\geq 2 \times$ ULN and ALP $< 2 \times$ ULN

ALT alanine aminotransferase; AST aspartate aminotransferase; TBL total bilirubin; ALP alkaline phosphatase; ULN upper limit of normal (value provided by the laboratory)

1. Elevations are from the same day

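### Adjudicated ALT/AST cases are given as a percentage of cases, so no planned table shows the at-risk percentage of elevations judged drug related

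*SAP*

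**What the plan says.** SAP 10.3 plans a table of subjects with an adjudicated case (ALT and/or AST at least 3 × ULN), which "will be summarized by treatment group and by relationship of ALT or AST elevation to study medication". Its denominator is set as follows: "The percentages will be calculated relative to the number of subjects with at least 1 adjudicated case". Its numerator is: "The numerator will be the number of subjects with at least 1 adjudicated case in the specific category of relationship". A subject with several cases is counted in one relationship category only.

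The paragraph just before it covers the hepatic criteria of SAP Appendix C, Table C-2 ("Criteria for Hepatic Laboratory Abnormalities") and uses a different base: "The percentages will be calculated relative to the number of subjects with at least 1 available postbaseline assessment". Those criteria include ALT or AST at least 3 × ULN, whatever the cause.

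SAP 10.3 also plans a listing of each adjudicated case with its liver enzyme values, relationship and confounding factors. Protocol 5.10 says that the adjudication committee's standardised process exists "in order to determine whether the elevation was related to atogepant".

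**The concern.** A table laid out by arm invites comparison between arms. Here each arm's denominator is itself an outcome of treatment, namely the number of its subjects who had a case. The categories then add to 100% in every arm that has a case, whether 1 subject or 10 were affected. The result answers how the cases in an arm divide by cause. It does not answer how often a treated subject had an elevation judged to be caused by the drug.

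No other planned display gives that second figure:

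- Table C-2 has an at-risk denominator but ignores cause.
- The tables of adverse events by relationship (SAP 10.2.3) use the investigator's assessment, not the committee's. Under Protocol 6.1 a laboratory abnormality becomes an adverse event only in certain circumstances.
- SAP 10.2.5 sends the hepatic events of special interest back to the laboratory section.
- The listing carries no rate.

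At stake is how easily the adjudicated result can be read across arms.

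**Working it through.** The documents state no figure on this point, so there is nothing to reproduce. The check compares the two denominators.

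**Inputs from the documents.** About 130 subjects per arm, randomised 1:1:1:1 (SAP 2.3), are used as an approximate at-risk number. The at-risk set for the double-blind period follows SAP 4.0: "Safety Population 1 consists of all subjects who received at least 1 dose of study drug during the double-blind treatment period". Protocol 2.2 says such elevations were rarely observed and gives no rate.

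**Assumptions.** The case counts, case rates (1% to 4% of an arm) and shares judged related (30% or 50%) are illustrative.

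**Formulas.** SAP percentage = related / adjudicated cases in the arm. At-risk percentage = related / subjects at risk in the arm.

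| Assumed counts (related of cases) | SAP rule | At risk, 130 per arm |
|---|---|---|
| Placebo 1 of 1; atogepant 2 of 4 | 100% vs 50% | 1/130 = 0.77% vs 2/130 = 1.54% |
| Placebo 2 of 4; atogepant 1 of 1 | 50% vs 100% | 1.54% vs 0.77% |
| Placebo 1 of 2; atogepant 2 of 6 | 50% vs 33.3% | 0.77% vs 1.54% |

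The order reverses in each row, in either direction.

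**Pooled reading.** If the denominator were the cases of both arms together, the first row would give 1/5 = 20% against 2/5 = 40%. The order is kept with equal arms, but the figure is still not an incidence.

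**Undefined percentages.** At a 1% case rate an arm of 130 has no case with probability 0.99^130 = 27%. The percentage is then 0/0. At 2% the probability is 0.98^130 = 7%.

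**How often the order reverses.** Cases are binomial with 130 per arm, and related cases are binomial among cases. A reversal means that atogepant has more related cases than placebo, both arms have a case, and the SAP percentage is strictly lower on atogepant.

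| Case rate, placebo vs atogepant | Share related (both arms) | Reversal, given more related cases on atogepant and a case in both arms | Reversal, among all trials |
|---|---|---|---|
| 1% vs 2% | 30% | 8% | 2% |
| 1% vs 2% | 50% | 19% | 6% |
| 1% vs 3% | 50% | 28% | 13% |
| 2% vs 4% | 50% | 28% | 17% |

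**Extension period.** Placebo completers are re-randomised 1:1:1, so each such group holds at most about 130/3 = 43 subjects, beside continuing groups of up to 130. If these groups are shown separately, as SAP 6.0 plans for exposure, one related case is 1/43 = 2.3% in one column and 1/130 = 0.8% in another. Counts alone then no longer show the order.

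**The case against.** The strongest reply is that the main hepatic safety quantity is already reported properly. The event of special interest is ALT or AST at least 3 × ULN regardless of cause, and Table C-2 gives exactly that on an at-risk denominator. In a randomised placebo-controlled trial, all-cause incidence by arm is also the comparison that needs no causality judgement. This stands, and it confines the gap to the related category. A reader might infer that the plan has no valid incidence for hepatic elevations; the documents do not support that.

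Second, the table states its base openly and prints counts beside percentages. With equal double-blind arms a careful reader sees 1 against 2 related cases and recovers the order, and every case is listed. This stands for the double-blind period. It is weaker in the extension if groups of unequal size are shown side by side.

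Third, a reader might infer that the committee exists to produce a per-arm incidence of related elevations. Protocol 5.10 describes a case-level determination within the atogepant programme and does not go that far.

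Fourth, the per-arm denominator is inferred, and the reversal rests on assumed counts. Both are true. The pooled reading would remove the reversal with equal arms, but it would still yield no incidence, and the silence on this point also needs correcting.

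Finally, the safety analyses are descriptive, and no test or decision rule in the documents uses this percentage. That also stands, and it limits the consequence to presentation.

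**Conclusion.** The point holds as a minor one. On the per-arm reading, the planned percentage is a distribution of causes among cases, can be undefined, and cannot be compared between arms as a risk. The only missing figure is the at-risk percentage of elevations adjudicated as related.

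It would be too strong to say that the table will mislead or would hide a hepatic signal. Under the four assumed scenarios a reversal occurs in 2% to 17% of all trials, or in 8% to 28% of those where atogepant has more related cases and both arms have a case. The illustrative counts can make either arm look worse. These sizes depend on the assumed case rates, the assumed related shares, 130 subjects at risk per arm and the per-arm denominator. The documents give no rates with which to narrow them.

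**What to change.** In SAP 10.3, report n/N (%) of subjects with an adjudicated case by relationship category, treatment group and period. Take N as subjects in the relevant Safety Population with at least one postbaseline ALT/AST result, in line with the rule already used for Table C-2. If the present percentage is kept, label it as a distribution among cases and say whether its denominator is per arm or pooled.

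The cost is one sentence in the SAP and one column in a table shell. It needs no new data and changes no other analysis.
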